6.2. Secondary study parameter(s)

Primary caregiver burden, symptom burden and quality of life of patients will be analyzed longitudinally using joint models for longitudinal analyses per symptom. Due to the fragility of the population, censoring of data will increase over time. Therefore, we will control for death, as well as age, gender, primary diagnosis, and performance status. Additionally, subgroup analyses for gender, age and primary diagnosis will be conducted for each secondary study parameter.

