3. STUDY DESIGN

To determine the effect of the PR methodology, a pragmatic open-label multicenter cluster randomized controlled trial (cRCT) will be conducted in nursing teams working in primary care, from January 2024 to March 2026 in Utrecht, the Netherlands. We define a cluster as one nursing team in primary care, which is a group of registered nurses (RNs) and nurse assistants (NAs) collaborating within one home care organization and within the same district with support of specialized nurses (SN) and/or nurse practitioners (NPs). The trial consists of an intervention group and a control group. To enhance heterogeneity of usual care in the control groups and limit the risk of bias, randomization of the intervention will be conducted within one primary healthcare organization.

The intervention starts with the adequate identification of patients in need of palliative care by means of the surprise question “would I be surprised if this patient dies in the next year?”. If the answer to the question is “no”, the patient is suitable for receiving palliative care. After identification the PR methodology is followed by four phases. step 1: map out the individual situation, symptom burden and quality of life of the patient, step 2: summarize the current problems and develop a proactive policy plan, Step 3: evaluate the effect of the proactive policy plan on the symptom burden and quality of life of the patient, step 4: adjust the policy plan if necessary and continue evaluating. The Utrecht Symptom Diary – four dimensional (USD-4D) will be used to monitor the individual situation, symptom burden and quality of life of patients, as described in step 1. This is a Patient Reported Outcome Measure (PROM) and is validated in palliative care populations.

The nursing teams selected as control group will continue to provide usual care to patients with a life-limiting illness. We define usual care as “care that patients with a life-limiting illness, living at home, would be expected to receive as part of normal practice from that specific homecare organization”(29). To gain insight into normal practice of the control group, we will consult the organization’s current safety standards, guidelines, and protocols. Additionally, questions regarding normal practice will be asked during interviews with healthcare professionals.

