4.4 Sample size calculation

As concluded by Adams et al., there is always a certain degree of uncertainty in estimating the magnitude of the intraclass correlation coefficient (ICC) for cRCTs beforehand(32). Therefore, the following calculation aims to provide the most accurate estimate of the required sample size, in order to demonstrate an effect. Based on our experience required during KWASA, a pilot study, primary nursing teams identify on average twenty patients with a life expectancy of one year or less. Hence, we expect the inclusion of twenty patients per nursing team to be feasible during this study. To estimate the number of clusters as accurate as possible, we considered different ICCs and different effect sizes for the intervention group(I). We calculated the number of clusters necessary assuming a power of 80%, an alpha of 5%, an effect size of 30% in the control group (C) and an effect size of 40% and 60% in the intervention group. Table 1 shows an overview of the results of our calculations.

Table 1. Overview results sample size calculation with different ICC and effect size.

ICC	N patients	I	C	N clusters
0.02	20	0.4	0.3	26
0.01	20	0.4	0.3	23
0.005	20	0.4	0.3	21
0.001	20	0.4	0.3	20
0.02	20	0.6	0.3	5
0.01	20	0.6	0.3	4
0.005	20	0.6	0.3	4
0.001	20	0.6	0.3	4

* ICC = Intraclass correlation coefficient. N patients = Number of patients in the cluster.
I = Intervention group. C = Control group. N cluster = Number of clusters.

According to our calculation a total of 20 clusters in each arm is the best fit for this study, assuming an effect size of 40% and an ICC of 0.001. A higher ICC results in a limited number of extra clusters, therefore, a total of 800 patients divided into 40 clusters is in our opinion the most appropriate. All calculations have been conducted with help of a methodologist from the Julius Centre and by means of the ClusterPower package of RStudio (Vienna, Austria), version 2022.12.0+353.

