5.1.2. Secondary study parameters/endpoints

The Quality of life of patients is assessed at enrolment, at one, three and six months by means of the EORTC QLQ C15 pal(33). This is a 15-item questionnaire developed by the European Organisation for research and treatment of cancer Quality of Life Group. The questions are answered on a scale from 1 to 4, in which the number 1 refers to “not at all”, 2 refers to “a little”, 3 refers to “quite a bit” and 4 refers to “very much”. The EORTC QLQ C15 pal is a shorted version of the original EORTC QLQ C30 pal, which is specifically developed for palliative care. To optimize the feasibility of measures, this shortened version will be used to reduce the risk of missing items and decrease the burden on participating patients.

Symptom burden of patients is assessed at enrolment, at one, three and six months by means of the Utrecht Symptom Diary Four Dimensional (USD4D), which is a patient reported outcome measure (PROM)(34). The USD4D comprises of questions regarding the physical, psychological, social, and spiritual dimension, which are rated on a scale from 0-10 (0 = symptom is absent to 10 = severity symptom is the worst imaginable).

Primary caregiver burden is defined as the perceived burden of the individual that is faced with the primary responsibility of taking care of a disabled friend or loved one. The primary caregiver burden Is assessed at enrolment, one, three and six months by means of the Self Rated Burden Scale, which is a one item numerical scale answering the question “How do I perceive the care for my loved one at the moment?”(35–38). The question is answered on a scale of 0 to 10, in which 0 refers to “not at all straining” and 1 refers to “much to straining”. In

addition, the perceived burden of informal care (Dutch: Ervaren Druk Informele Zorg (EDIZ)) will be used, assessing aspects of informal care contributing to the perceived burden(39).

The EDIZ is developed for the use in caregivers of patients suffering from dementia at home, however, this measurement instrument is widely used to assess the level of burden of caregivers of patients with a life-limiting illness. This instrument contains 9 statements to which patients must answer “no!”, “no”, “more or less”, “yes” or “yes!”.

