Lastly, an assessment of demographic characteristics and perceived care burden on the primary caregiver is performed by the research team. Thereafter, at one-, three- and six-months perceived care burden is evaluated by telephone using the EDIZ rating scale. After each assessment the primary caregiver will be offered support of a NP, specialised in PC to talk about possible thoughts or concerns raised by completing the questionnaires.

Blinding:

In causal studies, blinding is performed ideally at participant, data collection and data analysis level. In this case, however, blinding at the analysis level is the only feasible.

- The participants are not blinded. Patients, primary caregivers, and the nursing teams will all be aware of their allocation to the intervention group, since the method Palliative Reasoning will be implemented in daily care.
- The data collection will not be performed blindly. Firstly, the data are collected by local nurses who are aware of their allocation. Secondly, the research team who is involved in training the participants are also aware of the allocation, which is necessary to ensure an in-depth exploration of the experiences of the nursing team

during the up-following qualitative part of this study. This part will be described in a different research protocol, which is part of phase 4 of this study.

- Data analysis will be performed blinded. The researcher performing the data analysis will be blinded for the group allocation using labels. The labels will be opened after the analysis.

Randomization and allocation:

The clusters will be randomized through a simple randomization method with the Clinical Trial Randomization Tool from the National Cancer Institute(40,41). To minimize the risk of allocation bias, we will stratify between both homecare organization. The teams are informed about their allocation by the research team.

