6. STATISTICAL ANALYSIS

6.1. Primary study parameter(s)

To determine the effect of the SMEtH-intervention on the perceived symptom control after 1 month of patients of each nursing team, a mixed effects logistic regression analysis will be conducted. We will control for the following baseline measurements: age, gender, primary diagnosis, and performance status. Missing data are imputed using multiple imputation (MICE package in R) or if necessary, Bayesian imputation and analysis (Joint AI package in R). The quantitative data will be presented as odds ratio and 95% confidence interval (CI) in tables and graphs for the visualization of the results. Additionally, all analyses of primary and secondary study parameters are conducted by means of the statistical program RStudio, version 2022.12.0+353. (Vienna, Austria), and are considered statistically significant if $\alpha \leq 0.05$.

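### Section 6.2 gives the secondary joint models no nursing-team effect and lists death among the adjustment variables, and 6.1 imputes one-month answers with no exception for patients who died

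*Protocol*

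**What the plan says.** Protocol section 3 sets the unit: "We define a cluster as one nursing team in primary care". Section 5.2, on randomisation, adds: "The clusters will be randomized through a simple randomization method". Section 4.4 sizes the trial with ICCs from 0.001 to 0.02, adopts 0.001, and accepts that "there is always a certain degree of uncertainty in estimating the magnitude of the intraclass correlation coefficient".

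Under section 6.2, caregiver burden, symptom burden and quality of life "will be analyzed longitudinally using joint models for longitudinal analyses per symptom". Two sentences follow: "Due to the fragility of the population, censoring of data will increase over time", then "Therefore, we will control for death, as well as age, gender, primary diagnosis, and performance status". No nursing-team effect, event submodel or random effect is described. Section 5.1.2 gives the schedule: "Symptom burden of patients is assessed at enrolment, at one, three and six months". Quality of life and caregiver burden follow the same schedule.

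For the primary outcome, section 6.1 says that "a mixed effects logistic regression analysis will be conducted". The same sentence refers to the patients of each nursing team but does not name the random effect. Section 6.1 then has missing data imputed, by multiple imputation or if necessary by a Bayesian method, and states no exception. Section 5.1.1, explaining the choice of one month, gives death as a cause of missing data.

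The SAP file is a data management plan. Its Plan Overview repeats the primary model and covariates without a random effect. Its section 2.5 ticks that a missing-data policy exists, and its section 6 lists an analysis plan. The content of neither is among the documents.

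**The concern.** Three gaps meet in two short paragraphs.

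1. **Team effect.** Patients of one team share staff, training and allocation. A joint model can carry a patient random effect and still ignore team. If it does, intervals for any contrast that carries team variation are too narrow, and the false-positive rate exceeds 5%.
2. **Death as an adjustment variable.** Death occurs after randomisation, but 6.2 lists it beside age, gender, diagnosis and performance status. If the arm changes mortality, conditioning on death can distort the arm difference in either direction. If it does not, the distortion is about zero.
3. **Imputation for the dead.** Sections 5.1.1 and 6.1 together send a one-month answer lost through death to imputation. A patient who died before one month has no answer to whether symptoms are under control, so it is unclear which patients the primary odds ratio describes.

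The trial enrols people expected to live less than a year and follows them for six months, so deaths will be common enough for the handling to need stating.

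**Working it through.** **Inputs from the protocol.** 20 patients per team, 20 teams per arm, 800 patients, 40% v 30%, ICC 0.001 to 0.02 (section 4.4 and Table 1). Two-sided 5% is used because sidedness is not stated.

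**Assumptions.** No ICC is given for the secondary scales, so the Table 1 values are borrowed. No within-patient correlation *r* is given, so 0.5 to 0.7 is used. No death rate is given.

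**The plan's own figure.** Take the smallest *k* teams per arm with 80% power in a cluster *t* test: df = 2(*k*−1), noncentrality 0.10/√[2×0.35×0.65×DE/(20*k*)], DE = 1+19×ICC. For 40% v 30% this gives *k* = 19.21, 20.56, 22.26 and 25.64 at ICC 0.001, 0.005, 0.01 and 0.02. Rounded up, these are Table 1's 20, 21, 23 and 26. The design therefore allows for clustering by team.

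**One time point, team ignored.** Standard errors are 1−1/√DE too small; type I error is 2[1−Φ(1.96/√DE)].

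| ICC | DE | SE too small by | Type I error |
|---|---|---|---|
| 0.001 | 1.019 | 0.9% | 5.2% |
| 0.005 | 1.095 | 4.4% | 6.1% |
| 0.01 | 1.190 | 8.3% | 7.2% |
| 0.02 | 1.380 | 14.9% | 9.5% |

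**Three follow-ups at ICC 0.02, patient effect kept, team effect stable over time.** Set the variance at one visit to 1. The mean of three visits has variance V = *r*+(1−*r*)/3, which is 0.667 (*r* = 0.5) or 0.80 (*r* = 0.7).

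- *Unadjusted follow-up mean.* Team share = 0.02/V = 0.030 or 0.025; DE = 1+19×share = 1.570 or 1.475; type I error 11.8% or 10.7%. If 18, 15 and 11 patients per team remain at one, three and six months (assumption), it is 10.6% or 9.8%.
- *Mean adjusted for the enrolment value (slope r).* Team share = 0.02(1−*r*)²/(V−*r*²) = 0.005/0.4167 = 0.0120, or 0.0018/0.31 = 0.0058; DE = 1.228 or 1.110; type I error 7.7% or 6.3%.
- *Change from enrolment.* A stable team effect cancels, leaving about 5%.

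Simulation at ICC 0.02 (40 teams, team ignored, 6,000 trials) gives 10.3–12.1%, 6.3–7.9% and 5.0–5.1% for these three contrasts. The algebra describes linear mixed models, not a full joint model.

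**Deaths and the primary outcome.** If 5–15% die within one month (assumption), 0.05×800 = 40 to 0.15×800 = 120 answers would be imputed for patients who died. With 40% v 30% among survivors, the odds ratio is (0.4/0.6)/(0.3/0.7) = 1.56. Counting death as not under control multiplies each proportion by (1 − death rate):

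- equal deaths of 5%, 10%, 15%: 38.0 v 28.5%, 36.0 v 27.0%, 34.0 v 25.5%; odds ratios 1.54, 1.52, 1.51
- deaths 8% v 12% (intervention v control): 36.8 v 26.4%; odds ratio 1.62
- deaths 12% v 8%: 35.2 v 27.6%; odds ratio 1.42

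These figures show how far the result depends on the handling of deaths. They do not measure any bias from imputation.

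**The case against.** The sentence in 6.2 lists adjustment variables, not every model term. It also leaves out arm, time and the patient random effect, which nobody supposes will be absent. A reader might infer that the trial will ignore clustering; the text shows only that a team effect is not specified. This stands, and the inflation above is conditional on team being left out.

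A reader might also take a type I error of 10–12% as the size of the problem. That needs the highest Table 1 ICC and an unadjusted follow-up mean. Section 6.2 does not name that contrast, and the scales are also measured at enrolment. The smaller figures for adjusted and change contrasts count equally, and at the adopted ICC the effect is negligible.

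On death, a joint model usually links the longitudinal outcome to time to death, and the censoring sentence gives that as the motive. A survival submodel is the likelier intention, so the documents do not support saying that death will be an ordinary covariate.

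On imputation, 5.1.1 explains the choice of time point and is not a data-handling rule. Imputing within arm from survivors, under missing at random, would leave the 1.56 essentially unchanged. It would therefore be wrong to infer that the primary odds ratio is biased. Nor does the text support saying that the primary model ignores team: 6.1 points to team through its model type and its reference to each team's patients.

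The missing-data policy and analysis plan mentioned in the data management plan may settle some of this. They cannot be checked, and they do not change what 6.1 and 6.2 tell an analyst to do.

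**Conclusion.** The point holds at moderate size. Section 6.2 should be corrected because, followed as written, it leaves the randomised unit out of the secondary models and places a post-randomisation event among the baseline covariates.

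If team is omitted and the Table 1 ICCs apply, type I error at one time point runs from 5.2% to 9.5%. At ICC 0.02 it is about 10–12% for an unadjusted follow-up mean, about 6–8% after adjustment for enrolment, and about 5% for change from enrolment with stable team effects. The protocol itself calls the ICC uncertain, so the secondary analysis should not rely on the smallest tabulated value.

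No size is claimed for the adjustment for death. For imputation, the fault is an undefined population behind the primary odds ratio, with no bias shown; the handling matters mainly if deaths differ by arm. The primary model's allowance for clustering is sound if its random effect is team.

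**What to change.** In section 6.2, add a nursing-team random intercept alongside the patient random effect. Enter death only as the event of the survival submodel and remove it from the covariate list.

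In section 6.1, name team as the random effect and keep team in the imputation model. Impute one-month answers only for patients alive at one month, and report deaths by arm. Add a sensitivity analysis that counts death before one month as symptoms not under control.

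The cost is a few sentences, a little more modelling work and slightly wider secondary intervals. Design and sample size stay as they are. The wording should be settled before outcome data are examined by arm.

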5.1.3. Other study parameters

The following demographic characteristics will be collected of all participating parties:

- Patient demographics: age, gender, marital status, education level, employment status (retired, unemployed, employed), (past) illness, type of employment (in the past), duration of illness, treatment, phase of illness, comorbidity, performance status (KPS), time under nursing care, number of visits per day/week. These demographics will be collected by means of a questionnaire at baseline.
- Primary caregiver demographics: age, gender, education level, role, employment status assessed at enrolment. These demographics will be collected by means of a questionnaire, at baseline, three, six and twelve months after enrolment.
- Nurse demographics participating in individual assessments: age, gender, education level, employment status (fulltime/parttime), duration of current employment at enrolment. These demographics will be collected by means of a questionnaire, at baseline, six and twelve months after enrolment.
- GP demographics: age, gender, employment status (fulltime/parttime), duration of current employment at enrolment. These demographics will be collected by means of a questionnaire, at baseline.
- Nursing team demographics: education level, local collaborations with GP and paramedics, symptom management practices at enrolment. These demographics will be collected by means of a questionnaire, at baseline, six and twelve months after enrolment.

The demographics mentioned above will also be used during the process evaluation that is part of phase four of this study.

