6.3. Other study parameters

To provide characteristics of patients, primary caregivers, individual nurses, nursing teams and GPs at baseline, descriptive statistics will be used and displayed in tables.

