7.2. Recruitment and consent

Recruitment and consent of participants takes place on multiple levels:

Home care organizations will be recruited from a convenience sample of existing cooperation partners of the University Medical Centre Utrecht and from interested home care organizations. Contact with the organizations will take place through mail and telephone. If directors of the organizations consent to participation, regional and team managers will be contacted for further information. Information regarding this study will be provided digitally and verbally, however, the local routing of consent can alter per organization depending on the structures of the organization.

After consent of the home care organizations, team managers will receive written information about the study and if a team is interested, an information session will be organized to provide detailed information. During and after the information session, nursing teams will have the opportunity to ask questions that arise from the provided information. Verbal and oral consent for participation of a nursing team will be given by each team manager of the corresponding team.

The attending nurse and a contact person of each nursing team will screen patients on eligibility, to ensure a structured patient selection. During the study period the cohort will be accessible for the enrolment of new patients that meet the inclusion criteria. Eligible patients will be approached and asked by the attending nurse to participate. In case of a positive response, the nurse will ask the patient for permission to share their contact details with the research team to receive further information regarding the study. Patients will receive oral and written information and detailed participant information forms. The need for additional information or questions arising from the provided information will be answered by the

researchers in person or by telephone. After obtaining the written informed consent of the patient and the primary caregiver, both will be enrolled in the study. In case of unwillingness to participate in the study by a family caregiver, a patient still can be enrolled if desired.

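### The caregiver-burden models in Protocol 6.2 share the adjustment list of the patient outcomes: it does not say whose age and gender are meant, and it omits caregiver role, which is collected

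*Protocol*

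**What the plan says.** Protocol 6.2 puts three secondary outcomes under one model: "Primary caregiver burden, symptom burden and quality of life of patients will be analyzed longitudinally using joint models for longitudinal analyses per symptom". It then gives one adjustment list: "Therefore, we will control for death, as well as age, gender, primary diagnosis, and performance status". It also plans subgroup analyses by gender, age and primary diagnosis for every secondary parameter, which includes caregiver burden.

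For the patient primary endpoint, Protocol 6.1 uses the same four baseline terms: "We will control for the following baseline measurements: age, gender, primary diagnosis, and performance status".

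The caregiver outcome is the caregiver's own rating, repeated over time (Protocol 5.1.2): "The primary caregiver burden Is assessed at enrolment, one, three and six months by means of the Self Rated Burden Scale". The nine-item EDIZ is used alongside it.

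Protocol 5.1.3 records caregiver characteristics: "Primary caregiver demographics: age, gender, education level, role, employment status assessed at enrolment". The only use that section 6 gives them is descriptive (6.3): "To provide characteristics of patients, primary caregivers, individual nurses, nursing teams and GPs at baseline, descriptive statistics will be used". Protocol 5.1.3 adds that the demographics also serve the process evaluation.

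On participation, Protocol 7.2 says: "In case of unwillingness to participate in the study by a family caregiver, a patient still can be enrolled if desired". The abstract in the SAP document, which is a data management plan, repeats only the covariates of the primary analysis and describes no caregiver model.

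**The concern.** Burden is the only outcome the protocol defines for caregivers. The main parameter in 5.1.1 names them but is defined as the patient's perception. The burden model therefore carries the trial's evidence on caregivers, yet its covariates appear to have been chosen for patients.

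Two things are at stake. The first is precision: who the caregiver is (for example partner or child, older or younger) may explain part of the variation in burden, and leaving that out widens the interval. The second is comparability. Teams are randomised, but caregivers enter afterwards. Protocol 5.2 tells teams their allocation and places team training before the patient and caregiver baseline assessments. Protocol 7.2 has the attending nurse approach patients, keeps enrolment open, and lets a caregiver decline while the patient takes part. The caregivers analysed are thus a partly self-selected group reached through unblinded teams, and their mix may differ by arm. Age, gender and role at enrolment are suitable for adjustment because the intervention cannot plausibly change them.

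**Working it through.** **1. Whose values are in the list?** The terms set against Protocol 5.1.3:

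| Term | In the 6.2 list? | Whose value |
|---|---|---|
| Death | yes | patient (6.2 motivates it by the fragility of the population) |
| Primary diagnosis | yes | can only be the patient's |
| Performance status | yes | patient; recorded among patient demographics ("comorbidity, performance status (KPS), time under nursing care, number of visits per day/week") |
| Age, gender | yes | recorded for both patient and caregiver; 6.2 does not say which |
| Caregiver role | no | recorded for the caregiver; absent on either reading |

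The match with 6.1 favours the patient's age and gender. If the caregiver's were meant, role would still be missing.

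**2. The plan's own figure.** There is none for caregiver burden: no SD, effect, power or number of caregivers. The only sample size is for the patient endpoint (Protocol 4.4: 40% v 30%, 20 per cluster, ICC 0.001, 20 clusters per arm). It reproduces: (1.960 + 0.842)² × (0.24 + 0.21) × (1 + 19 × 0.001) / (0.10² × 20) = 18.0 clusters. With a t correction this becomes 19.01, rounded up to 20. The present point does not rest on it.

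**3. Precision.** SE ratio = √(1 − R²), where R² is the share of burden variance that caregiver traits explain beyond the covariates already in the model. The R² values are assumptions.

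| Additional R² | SE ratio | Power, if it was 80% before |
|---|---|---|
| 0.02 | 0.990 | 80.8% |
| 0.05 | 0.975 | 82.0% |
| 0.10 | 0.949 | 84.0% |
| 0.15 | 0.922 | 86.0% |

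Power = Φ(2.802 / √(1 − R²) − 1.960). The SE therefore falls by 1.0% to 7.8%. In a repeated-measures model, fixed traits reduce only the between-person part of the variance, so the upper rows are generous.

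**4. Mix.** Shift in a wholly unadjusted arm contrast = difference in share × effect of the trait. Assuming a 5 to 20 point difference in the share of partners and a 0.5 to 1.5 point role effect on the 0-10 scale, this gives 0.05 × 0.5 = 0.025 to 0.20 × 1.5 = 0.30 points. The planned model is not wholly unadjusted, so these figures illustrate the mechanism and do not estimate its bias.

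**5. Could chance alone produce such a difference?** Assume 60% partners, 200 to 400 caregivers per arm, ICC 0.001 to 0.02 and 20 per cluster. SE of the difference in share = √(2 × 0.6 × 0.4 × (1 + 19 × ICC) / n). For n = 400 and ICC 0.001 this is √(0.48 × 1.019 / 400) = 0.035. For n = 200 and ICC 0.02 it is √(0.48 × 1.38 / 200) = 0.058. A 10-point difference is thus 1.7 to 2.9 SEs (10/5.8 to 10/3.5), which would be uncommon by chance. Larger differences would come mainly from enrolment that differs by arm.

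**The case against.** The strongest reply is that this is an ambiguity and not a stated choice. The list could mean the respondent's age and gender plus the patient's diagnosis and performance status, which is close to what is asked for here. A reader might infer that 6.2 prescribes the patient's age and gender for caregiver burden. The text does not settle that, although the repetition of the 6.1 list makes it the more natural reading. The reply does not dispose of the point, because role is missing either way and the subgroup definitions are equally unclear.

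A second reply is that patient diagnosis and performance status are reasonable predictors of caregiver burden, and that patient age and gender may be related to whether the caregiver is a partner or a child. This stands: the list is incomplete, not useless, and may correct some of an imbalance.

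Third, burden is measured at enrolment and modelled over time, which could absorb much of a stable difference between caregiver types. That is fair as far as it goes, but 6.2 does not say how enrolment burden enters. In the intervention arm it may also already be affected, since 5.2 puts training before baseline and SAP 2.4 places quantitative data collection after implementation.

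Finally, a reader might infer that the caregiver data go unused. They do not: 5.1.3 assigns them to the process evaluation as well. The accurate statement is that section 6 gives them no role in estimating the effect.

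**Conclusion.** The point holds as a minor, free improvement to a secondary analysis. Section 6.2 should say whose age and gender it means for caregiver outcomes, and its list lacks caregiver role on any reading.

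Its size cannot be derived from the documents and is probably modest: an SE about 1-8% smaller if caregiver traits add 2-15% to the explained variance, which is an assumption. A reader might go further and conclude that the caregiver results will be biased, or that a definite amount of precision is lost. The documents support neither. They show a route by which caregiver mix could differ by arm, not that it will. Any bias depends on selective enrolment and on the handling of enrolment burden. Adjustment would remove only differences in the traits measured. The primary analysis is not affected.

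**What to change.** In Protocol 6.2, give the Self Rated Burden and EDIZ models their own list:

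- keep the control for death and the patient's primary diagnosis and performance status;
- add the caregiver's age, gender and role, taken from the enrolment questionnaire (5.1.3 also schedules later collections, so the time point should be named);
- state that the age and gender subgroups for caregiver outcomes use the caregiver's values.

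Leave the list for the patient outcomes unchanged. It would also help to state in 6.2 how enrolment burden enters the model. The change takes a sentence or two of text and a few extra model terms. It needs no new data and adds no burden for participants. Made before analysis, it avoids a choice of covariates after the data are seen.
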